6.4. Patient Characteristics

A summary table will be generated for patient and diabetes characteristics at study entry using all treated patients. The following variables will be included but not limited to: age, age groups (<65 , ≥ 65 years), sex, ethnicity, race, height, weight, body mass index (BMI), BMI group (<25 , ≥ 25 to <30 , ≥ 30 to <35 , ≥ 35 kg/m²), duration of diabetes, participant's prior CGM use, Use of SGLT2, Use of injectable GLP-1, prandial dosing plan (carbohydrate counting/fixed dose), HbA1c at study entry and baseline.

For continuous variables, the following statistics will be provided: mean, SD, minimum, maximum, and median. For categorical variables, summary statistics will include sample size, frequency and percentage. A listing of patient characteristics at study entry will be provided.

For all treated patients, the number and percentage of patients with preexisting conditions will also be summarized using Medical Dictionary for Regulatory Activities (MedDRA) preferred term (PT) nested within system organ class (SOC). Preexisting conditions are conditions that are still ongoing at inform consent. Events will be ordered by decreasing frequency.

6.5. Treatment Compliance

No analysis for treatment compliance is planned for this study.

6.6. Important Protocol Deviation

Important protocol deviations (IPD) that potentially compromise data integrity or patients' safety will be summarized for all treated patients. The listing of important protocol deviations for all treated patients during the entire study will be provided in the CSR. The IPDs identified by site monitoring and clinical database will be integrated in the listing. If the IPD is identified by both methods, only the site monitoring IPD will be presented.

6.7. Concomitant Therapy

Concomitant medication will be summarized for the treated population during the treatment periods (0 to 12 weeks). The percentages of patients receiving each concomitant medication will be summarized using PT nested within Anatomical Therapeutic Chemical (ATC) Level 3 code. Medications will be ordered by decreasing frequency within ATC level. Concomitant medication used during the baseline period will also be summarized for the enrolled population.

The daily basal dose, daily bolus dose, total insulin dose, and the ratio of bolus dose to total insulin dose during the baseline period will be summarized. The doses and bolus/total insulin dose ratios for each visit will be calculated as the mean of the doses for the last 3 days prior to the visit date that are entered in the electronic case report form (eCRF). Doses will be summarized in U and U/kg.

6.8. Efficacy Analyses

6.8.1. Primary Endpoint

The primary efficacy comparison will be based on the MMRM analysis of change from baseline in time in target range (70-180 mg/dL [3.9-10.0 mmol/L]) during daytime period including data collected prior to permanent discontinuation of IP. The analysis model and selection of covariance structure is described in Section [6.2](#).

6.8.2. Gated/Other Secondary Endpoints

The analysis of the secondary gated objectives will be conducted if the time in target range (70-180 mg/dL [3.9-10.0 mmol/L]) during the daytime period at study endpoint versus baseline is found statistically significant for the primary efficacy analysis at a 2-sided 0.05 significance level (Westfall and Krishen 2001). If this contrast is significant, the secondary objectives were tested in sequence until the first null hypothesis in the sequence failed to be rejected at a 2-sided 0.05 significance level. The sequential testing for gated secondary objectives is conducted in the following order to assess whether value at study endpoint is superior to baseline:

1. To evaluate HbA1c
2. To evaluate time glucose values from CGM are within target range (70-180 mg/dL [3.9-10.0 mmol/L]) during the 24-hour period.

For continuous longitudinal secondary endpoints, the MMRM model similar to that for the primary analysis will be used. Duration and percent time in range, time in hypoglycemia, and time in hyperglycemia derived from CGM data will also be analyzed using an MMRM model. Details for the CGM analyses can be found in Section [6.10](#).

Continuous nonlongitudinal secondary endpoints will be analyzed using the ANCOVA. Postprandial incremental area under the curve (AUC)₀₋₁ hour and incremental AUC₀₋₂ hour will be analyzed by ANCOVA described in Section [6.2](#).

Proportion of participants with HbA1c <7.0% and \leq 6.5% will be analyzed using a longitudinal logistic regression with repeated measurements conducted by a generalized linear mixed model with the fixed class effect of visit, the covariate of baseline HbA1c, and the random effect of participant.

Actual and change from baseline in basal, bolus, and total dose, as well as the bolus/total insulin dose ratio will be analyzed by the MMRM models described in Section [6.2](#).

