9.4.3. Gated/Other Secondary Endpoints

The analysis of the secondary gated objectives will be conducted if the time in target range (70-180 mg/dL [3.9-10.0 mmol/L]) during the daytime period at study endpoint versus baseline is found statistically significant for the primary efficacy analysis at a 2-sided 0.05 significance level (Westfall and Krishen 2001). If this contrast is significant, the secondary objectives were tested in sequence until the first null hypothesis in the sequence failed to be rejected at a 2-sided 0.05 significance level. The sequential testing for gated secondary objectives is conducted in the following order to assess whether value at study endpoint is superior to baseline:

1. To evaluate HbA1c
2. To evaluate time glucose values from CGM are within target range (70-180 mg/dL [3.9-10.0 mmol/L]) during the 24-hour period.

For continuous longitudinal secondary endpoints, the MMRM model similar to that for the primary analysis will be used. Duration and percent time in range, time in hypoglycemia, and time in hyperglycemia derived from CGM data will also be analyzed using an MMRM model. Continuous nonlongitudinal secondary endpoints will be analyzed using the ANCOVA.

Postprandial incremental area under the curve (AUC)₀₋₁ hour and incremental AUC₀₋₂ hour will be analyzed by ANCOVA. Analysis details will be documented in the SAP. Proportion of participants with HbA1c <7.0% and ≤6.5% will be analyzed using a longitudinal logistic regression with repeated measurements conducted by a generalized linear mixed model with the fixed class effect of visit, the covariate of baseline HbA1c, and the random effect of participant. Actual and change from baseline in basal, bolus, and total dose, as well as the bolus/total insulin dose ratio will be analyzed by the MMRM models described in Section [9.4.1](#).

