
 To evaluate time in hypoglycemic glucose ranges, obtained from CGM use 	
 Percentage of time with CGM glucose values <54 mg/dL (<3.0 mmol/L) during daytime and 24-hour periods with 14 days of CGM use at Week 12 compared with baseline

 To evaluate time in hyperglycemic glucose ranges, obtained from CGM use 	
 Percentage of time with sensor glucose values >180 mg/dL (>10.0 mmol/L) and >250 mg/dL (>13.9 mmol/L), during daytime and 24-hour periods with 14 days of CGM use at Week 12 compared with baseline

 To evaluate postprandial incremental AUCs, obtained from CGM use 	
 Postprandial incremental $AUC_{0-1\text{ hour}}$ and incremental $AUC_{0-2\text{ hour}}$ at Week 12 compared with baseline

 To evaluate proportion of participants achieving HbA1c targets 	
 The proportion of participants with $HbA1c < 7\%$ and $\leq 6.5\%$ at Week 12

 To evaluate bolus, basal, and total daily insulin dose 	
 Bolus, basal, and total insulin doses and bolus/total insulin ratio at Week 12 compared with baseline

 To evaluate severe hypoglycemia 	
 Incidence of severe hypoglycemia events from baseline to Week 12

 To evaluate insulin treatment satisfaction regarding glycemic control as measured by the ITSQ 	
 Change from baseline in ITSQ glycemic control domain scores at Week 12
Tertiary/Exploratory	

 To evaluate proportion of participants achieving CGM-based glycemic targets 	
 The proportion of participants with percentage of time in target CGM glucose range ($70-180\text{ mg/dL}$ [$3.9-10.0\text{ mmol/L}$]) $>70\%$, time in hypoglycemia ($<54\text{ mg/dL}$ [$<3.0\text{ mmol/L}$]) $<1\%$, and time in hyperglycemia ($>250\text{ mg/dL}$ [$>13.9\text{ mmol/L}$]) $<5\%$ with 14 days of CGM use at Week 12

 To evaluate glucose profiles, obtained from CGM use 	
 Average glucose for a 24-hour period from each 14-day CGM session at Week 12 compared with baseline

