6.2. General Considerations

Statistical analysis of this study will be the responsibility of Lilly or its designee. Any change to the data analysis methods described in the protocol will require an amendment ONLY if it changes a principal feature of the protocol. Any other change to the data analysis methods described in the protocol, and the justification for making the change, will be described in the statistical analysis plan (SAP) or the clinical study report (CSR). Additional exploratory analyses of data will be conducted as deemed appropriate.

Efficacy analyses will be conducted on the treated population, including data collected prior to permanent discontinuation of IP. When change from baseline is included as a *response variable of analysis models*, the participant will be included in the analysis only if a baseline and a postbaseline measurement are available.

Safety analyses will be conducted on the treated population. Analyses of adverse events (AEs) and severe hypoglycemia will include data collected during the treatment period and baseline period. Adverse events during the follow-up period will be listed.

Unless otherwise noted, all tests will be conducted at a 2-sided alpha level of 0.05, and confidence intervals (Cis) will be calculated at 95%, 2-sided. A gatekeeper method (Westfall and Krishen 2001) will be used to control the overall type 1 error for the primary and gated secondary objectives.

Baseline is defined as the last nonmissing measurement at or before Visit 4 unless otherwise specified.

A restricted-maximum-likelihood-based, mixed model repeated measures (MMRM) analysis will be used to analyze continuous longitudinal variables. All the longitudinal observations at each scheduled postbaseline visit will be included in the analysis. The model for the analysis of the primary efficacy endpoint of change from baseline in time in target range (70-180 mg/dL [3.9-10.0 mmol/L]) during daytime period will include the fixed class effect of visit, the covariate of baseline, and the random effect of participant. An unstructured covariance structure will be used to model the within-participant errors. Significance tests will be based on least-squares means and Type III tests. SAS® PROC MIXED will be used to perform the

analysis. If this analysis fails to converge, the following covariance structures will be tested in order:

- Toeplitz with heterogeneity
- autoregressive with heterogeneity

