- compound symmetry with heterogeneous variances
- Toeplitz
- autoregressive
- compound symmetry without heterogeneous variances

The first covariance structure that converges will be used. The Kenward-Roger approximation will be used to estimate denominator degrees of freedom.

An analysis of covariance (ANCOVA) will also be used to analyze continuous variables collected only at baseline and endpoint. The model will include baseline as a covariate. Unless otherwise stated, missing endpoints will be imputed using the last-observation-carried-forward (LOCF) approach, using only postbaseline data.

For continuous measures, summary statistics will include sample size, mean, standard deviation (SD), median, minimum, and maximum for both the actual and the change from baseline measurements. Least-square means and standard errors derived from the analysis models will also be displayed for the change from baseline measurements.

For categorical measures, summary statistics will include sample size, frequency, and percentages.

Table ITSW.6.1. Baseline and Post-Baseline Definitions and Patient Population by Type of Analysis

Analysis	Patient Population	Baseline Observations	Post-Baseline Observations
HbA1c MMRM	All treated patients with a baseline and at least one post-baseline observation	Last of Visits 1-4	Visits 7, 9, and 12 prior to discontinuation of IP
HbA1c categorical analysis longitudinal logistic regression	All treated patients with a baseline and at least one post-baseline observation	Last of Visits 1-4	Visits 7, 9, and 12 prior to discontinuation of IP
CGM outcomes	All treated patients with a baseline and at least one post-baseline observation	Visit 4	Visits 7, 9, and 12 prior to discontinuation of IP
Basal, bolus, and total insulin doses, and bolus/total insulin dose	All treated patients with a baseline and at least one	Visit 4	Visits 6, 7, 9, and 12 prior to discontinuation of IP

ratios continuous analysis	post-baseline observation		
Health outcomes: ITSQ, DSAT	All treated patients with a baseline and a post-baseline observation	Last of Visits 2-4	Visit 12 prior to discontinuation of IP
Health outcome: Study mealtime insulin experience question	All treated patients with a post-baseline observation	NA	Visit 12 prior to discontinuation of IP
Weight and vital signs	All treated patients with a baseline and at least one post-baseline observation	Last of Visits 1-4	Visits 7, 9, and 12 prior to discontinuation of IP

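### Must the SAP name the model quantity reported for the Week 12 HbA1c-target proportions?

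*SAP*

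**What the plan says.** SAP Table ITSW.4.1 lists, among the other (ungated) secondary objectives, "To evaluate proportion of participants achieving HbA1c targets". The endpoint is the proportion below 7% and the proportion at or below 6.5% at Week 12.

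SAP 6.8.2 specifies a longitudinal logistic regression fitted as a "generalized linear mixed model with the fixed class effect of visit, the covariate of baseline HbA1c, and the random effect of participant". Protocol 9.4.3 has the same sentence: "longitudinal logistic regression with repeated measurements conducted by a generalized linear mixed model with the fixed class effect of visit". In Table ITSW.6.1 the row "HbA1c categorical analysis longitudinal logistic regression" adds the population, the baseline and the post-baseline visits ("Visits 7, 9, and 12 prior to discontinuation of IP"), but no output.

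SAP 6.2 has two display rules. In the paragraph on continuous measures: "Least-square means and standard errors derived from the analysis models will also be displayed for the change from baseline measurements". For categorical measures: "For categorical measures, summary statistics will include sample size, frequency, and percentages".

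**The concern.** The endpoint is a population proportion, but the named model is subject-specific and on the logit scale. The study has one arm, so there is no treatment odds ratio to report, and a reader may expect the model's output to be the Visit 12 least-squares mean turned back into a probability. That figure differs from the population proportion for two separate reasons:

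- **Random effect.** If the participant effect is a random intercept, the least-squares mean sets it to zero. The inverse logit is not linear, so the probability at the average participant is not the average probability.
- **Baseline.** The figure is evaluated at mean baseline HbA1c, not averaged over the observed baselines. This remains if the repeated measures are handled by GEE or a residual covariance.

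Below 50%, both push the figure down. The report could then carry a model estimate and confidence interval visibly at odds with the observed percentage, most likely for the rarer ≤6.5% target.

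**Working it through.** **The plan's own figures.** The documents give no expected proportion, random-effect SD or visit correlation for this endpoint. The only design figures concern the primary endpoint, and they reproduce: 4.5/(19.5/√150) = 2.826, and Φ(2.826 − 1.96) = 0.807, against a stated 80%; 150/0.9 = 166.7, hence 167. They do not bear on this point. Everything below rests on assumed inputs.

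**Random effect alone.** For true proportion p and random-intercept SD σ, solve for a in ∫ expit(a + σu) φ(u) du = p. The printed figure would be expit(a). For p = 30% and σ = 2, a = −1.384 and expit(a) = 20.0%.

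| True p | σ = 1 | σ = 2 | σ = 3 |
|---|---|---|---|
| 15% | 11.4% | 6.0% | 2.6% |
| 30% | 26.5% | 20.0% | 13.9% |
| 50% | 50% | 50% | 50% |

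The gap is zero only at exactly 50%. At 52.3% with σ = 3.8 the printed figure is 56.0%.

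**Baseline alone.** Take Week 12 HbA1c as normal with mean μ and SD 0.85, correlated ρ with baseline. With cut-off c (6.95 for <7%, 6.55 for ≤6.5%, values being recorded to 0.1), the population proportion is Φ((c − μ)/0.85). The probability at mean baseline is Φ((c − μ)/(0.85√(1 − ρ²))). For μ = 7.4, c = 6.95 and ρ = 0.5: (6.95 − 7.4)/0.85 = −0.529, giving 29.8%; −0.529/0.866 = −0.611, giving 27.0%.

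| μ, target | Population | ρ = 0.3 | ρ = 0.5 | ρ = 0.7 |
|---|---|---|---|---|
| 7.4, <7% | 29.8% | 28.9% | 27.0% | 22.9% |
| 7.4, ≤6.5% | 15.9% | 14.7% | 12.4% | 8.1% |
| 6.9, <7% | 52.3% | 52.5% | 52.7% | 53.3% |

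**Both together.** A second set of assumptions used baseline HbA1c normal (mean 8.5, SD 0.7) truncated to 7.5–10, and a slope of −1.5 logits per 1% HbA1c. A true 20% becomes 16.9% from baseline alone, 9.7% from a random-effect SD of 2 alone, and 8.7% from both. Averaging the predictions over the random effect and the baselines returns 20%.

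**Does the plan lead there?** The mathematics is sound, so the question is whether the SAP sends the analyst to that figure. Its least-squares-mean rule is confined to change from baseline in continuous measures, and its rule for categorical measures is observed counts and percentages. Followed as written, the plan produces the Week 12 percentage. In a simulation with 10% random dropout and a true 29.8% below 7%, the observed percentage averaged 29.7% to 30.2%, so the planned descriptive figure is on target.

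**The case for a change.** The best case for a change is this. Protocol 9.4.1 promises more technical detail in the SAP, yet SAP 6.8.2 repeats the protocol sentence. It says the proportion will be analysed by the model, so a model result is expected beside the percentage, and nothing says which of the two is the endpoint result. They also use different participants: the model admits anyone with a baseline and one post-baseline value, while an observed Week 12 percentage needs a Week 12 value. In one assumed scenario with dropout related to Visit 7 HbA1c and a true 29.8%, observed n/N gave 32.3% and the averaged maximum-likelihood model 30.9%. Clarification would take a sentence or two and no amendment, since a change "will require an amendment ONLY if it changes a principal feature of the protocol".

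The silence is real, and so is the difference between the two quantities. The rest carries less weight:

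- Visit odds ratios or a Type III test of visit fit the SAP's wording as well as a back-transformed mean does.
- A probability at mean baseline is a legitimate conditional quantity. Simulated coverage of 64% to 88% for its interval (GEE and pseudo-likelihood) scores it against a target it does not estimate.
- The larger gaps assume a Week 12 mean of 7.4%, which has no source in the documents. The nearest figure is the 6.92% Week 26 mean for LY900014 in the earlier type 2 trial (Protocol 2.2). It is only indicative, as the duration differs, but it puts the <7% target near 50%. The random-effect gap still does not vanish there: simulated maximum-likelihood figures were 53.7% to 57.4% against 52.2% to 52.8% observed.
- Screening HbA1c is restricted to 7.5–10% (Protocol 5.1). Truncating the assumed baseline to that range lowers a correlation of 0.50 to 0.41 and weakens the baseline effect.
- The dropout scenario favours the averaged model by 32.3 − 30.9 = 1.4 points, on an invented mechanism.

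**Conclusion.** The SAP leaves an output detail open, but no stated rule is wrong. The endpoint is a Week 12 proportion, and the observed frequency and percentage already planned in SAP 6.2 answer it. An analyst would report n/N with its denominator and, if a model-based probability were added, would either label it as conditional or average it over the random effect and baselines. That is table-specification work.

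The possible discrepancy ranges from nothing to more than ten points (30% printed as 13.9% at a random-effect SD of 3), but it arises only if a quantity the plan never promises is printed and read as the population proportion. Its size depends on a random-effect SD, a baseline correlation and a true proportion that the documents do not give. The endpoint is ungated, there is no comparison between arms, and neither the primary result nor the gated sequence depends on it. No change to the plan is called for.

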6.8.3. Analyses of Exploratory Efficacy and Health Outcomes Objectives

Proportion of patients who have achieved the below recommended individual and composite CGM targets (Battelino 2019) of glycemic control at Visit 12 (10 - 12 weeks) will be summarized:

- percentage of time in target CGM glucose range (70-180 mg/dL [3.9-10.0 mmol/L]) $>$ 70%

- percentage of time in hypoglycemia (<54 mg/dL [<3.0 mmol/L]) $<1\%$
- percentage of time in hyperglycemia (>250 mg/dL [>13.9 mmol/L]) $<5\%$

In addition, proportion of patients who have achieved the below recommended individual CGM targets of glycemic control at Visit 12 (10 - 12 weeks) will be summarized:

- percentage of time in hypoglycemia (<70 mg/dL [<3.0 mmol/L]) $<4\%$
- percentage of time in hyperglycemia (>180 mg/dL [>13.9 mmol/L]) $<25\%$

Average glucose for a 24-hour period from each 14-day CGM session at Visit 12 (10 - 12 weeks) and baseline (-2-0 weeks) will be analyzed by ANCOVA described in Section 6.2.

Within-day and between-day glycemic variability measured by the SD and the coefficient of variation (CV) of CGM data will also be analyzed by the ANCOVA model specified in Section 6.2. Details for the glycemic variability derivation can be found in [Appendix 1](#).

In addition, CGM outcomes that are not included in the primary or secondary efficacy endpoints will be analyzed as exploratory efficacy endpoints. Details for the CGM analyses can be found in Section 6.10.

For the ITSQ, the change from baseline to LOCF endpoint while on treatment in each domain transformed score (inconvenience, lifestyle, hypoglycemic control, glycemic control, and delivery system) and overall transformed score will be analyzed using ANCOVA.

For the DSAT, the change from baseline to LOCF endpoint, while on treatment, in each item and a total score will be analyzed using ANCOVA.

Summary statistics, including number of participants and proportion of a categorical outcome (5 levels) for the study mealtime insulin experience question will be provided.

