Appendix 1. Derivation of CGM Variables

General Derivation Specifications

All CGM variables will be derived for each patient, for each valid CGM day and also overall for baseline (Week -2-0), Visit 7 (Week 2-4), Visit 9 (Week 6-8), and Visit 12 (Week 10-12).

No missing CGM values will be imputed.

Since the CGM values may not be measured at the exact same time for each day for a specific individual patient, due to device changes or gaps in usage, non-overlapping intervals ('buckets') of 15 minutes over 00:00:00 to 23:59:59 (00:00:00 to 00:14:59, 00:15:00 to 00:29:59, etc.) will be used for any derivations requiring time-matched measurements across days within a visit.

All CGM glucose derivations will be conducted in units of mg/dL and will be converted to mmol/L by multiplying by 0.0555.

Only readings from valid CGM days (defined in Section 6.10.1) collected during the entire baseline period and treatment period will be included in derivations, excluding data (if any) that are collected while patients temporarily are off study treatment.

Glucose in Target Ranges, Hypoglycemia- or Hyperglycemia

The percentage of time within a glucose range (target, hypo- or hyperglycemia ranges) will be calculated as the number of observations within the specified range divided by the number of observations in the time interval (e.g., 24-hour period). The duration (in minutes) within the glucose range will then be calculated as the percentage of time within the glucose range times the length of the period (24 hours, 18 hours, for the periods of 24-hour or daytime respectively).

For example, if a patient had a total of 5 observations with glucose values <70 mg/dL (3.9 mmol/L) out of a total of 90 observations recorded in a 24-hour period, the percentage of time spent in hypoglycemia during the 24-hour period for this patient will be calculated as 5/90 = 5.6%. The duration (in minutes) with hypoglycemia (glucose value <70 mg/dL [3.9 mmol/L]) during this 24-hour period for this patient will be calculated as the percentage of time within the glucose range times the length of the period 1440 minutes (24 hours), (i.e., 5/90*1440 = 80 minutes).

Incremental Area under the Glucose Curve (iAUC)

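### 24-hour mean glucose and glucose variability go to a two-point ANCOVA with default LOCF although Visit 7 and 9 values exist, and the ITSQ, DSAT and iAUC endpoint rules do not match Table ITSW.6.1

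*SAP*

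**What the plan says.** **General rule.** SAP 6.2 has two models for continuous variables. For repeated measures, a "mixed model repeated measures (MMRM) analysis will be used to analyze continuous longitudinal variables". For the rest: "An analysis of covariance (ANCOVA) will also be used to analyze continuous variables collected only at baseline and endpoint". The ANCOVA has a default for missing data: "missing endpoints will be imputed using the last-observation-carried-forward (LOCF) approach, using only postbaseline data", unless the SAP states otherwise.

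**CGM mean glucose and variability.** SAP 6.8.3 says that 24-hour average glucose at Visit 12 and baseline "will be analyzed by ANCOVA described in Section 6.2", and it assigns within-day and between-day SD and CV to the same model. SAP 6.10.1 limits CGM variables other than the time-in-range family to baseline and Visit 12. Appendix 1, however, says "All CGM variables will be derived for each patient, for each valid CGM day and also overall for baseline", and goes on to name Visits 7, 9 and 12. The CGM row of Table ITSW.6.1 also lists Visits 7, 9 and 12.

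**ITSQ and DSAT.** SAP 6.8.3 and protocol 9.4.6.1 analyse change to an LOCF endpoint while on treatment. The Table ITSW.6.1 row for these scales allows only "Visit 12 prior to discontinuation of IP". The Schedule of Activities collects both scales at Visits 2, 4 and 12 and at early discontinuation.

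**iAUC.** SAP 6.8.2 sends iAUC to the 6.2 ANCOVA, so LOCF applies by default. Its row in Table ITSW.6.1 admits Visit 12 only.

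**The concern.** Mean glucose, SD and CV come from a sensor worn from Visit 2 to Visit 12, so they do not meet the SAP's own criterion for ANCOVA. If the 6.2 default is followed, a Week 2-4 or Week 6-8 value stands in for Week 12 in a participant who leaves early. If it is not followed, the analysis uses completers only and the Visit 7 and 9 data go unused. Time in range, from the same readings in the same people, goes to an MMRM that uses all three visits. Two summaries of one glucose trace would then rest on different treatments of dropout.

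For ITSQ and DSAT, the text and the table define different analysis sets. The ITSQ glycemic control domain is a listed secondary endpoint, as is iAUC, where the rule is also unsettled. In an open-label, single-arm study the choice should not be left until the results are visible.

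**Working it through.** **1. The plan's own figures.** Inputs from SAP 5.2: detectable change 4.5, SD 19.5, 150 completers, 10% dropout, two-sided alpha 0.05. Normal approximation: 4.5 × √150 / 19.5 = 2.826; Φ(2.826 − 1.960) = 80.7%. The noncentral t gives 80.2%. Number assigned: 150 / 0.90 = 166.7, so 167. The stated power and size reproduce, and nothing below changes them.

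**2. Which model does 6.2 assign?**

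| Variable | Post-baseline values available | Model under the 6.2 criterion | Model stated |
|---|---|---|---|
| Time in range (daytime, 24-hour) | Visits 7, 9, 12 | MMRM | MMRM (6.8.1, 6.8.2) |
| 24-hour mean glucose; within- and between-day SD, CV | Visits 7, 9, 12 (Appendix 1) | MMRM | ANCOVA (6.8.3) |
| ITSQ, DSAT | Visit 12, early discontinuation | ANCOVA | ANCOVA, LOCF endpoint (6.8.3) |
| iAUC | Visits 7, 9, 12 by Appendix 1; Visit 12 only by Table ITSW.6.1 | depends on which text governs | ANCOVA (6.8.2; protocol 9.4.3) |

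Overall variability is computed over Weeks 0-12 (Appendix 1), so it has no visit-level values and lies outside this comparison.

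**3. What LOCF can carry for ITSQ and DSAT.** The only post-baseline collections are Visit 12 and early discontinuation. Under the table there is nothing to carry. Under the text the only value that can be carried is the early discontinuation score, which the table leaves out. The two rules therefore differ by exactly the participants who leave early and complete the scales at that visit while on treatment.

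**4. How many participants.** 167 − 150 = 17, and 17/167 = 10.2%. This is an upper bound, because leavers without a usable post-baseline value enter under neither rule. If all 17 had one, moving from LOCF to Visit 12 only would raise the standard error by a factor of √(167/150) = 1.055.

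**5. Size of the LOCF effect on mean change.** The documents do not give the effect at Visits 7 or 9. Assume that a share d of participants has a carried value, that the carried value shows a fraction f of the Week 12 effect, and that leavers would have reached the same Week 12 effect as completers. The expected LOCF estimate as a fraction of the true change is 1 − d(1 − f).

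| d | f = 0.25 | f = 0.50 | f = 0.75 | f = 1 |
|---|---|---|---|---|
| 5% | 96.3% | 97.5% | 98.8% | 100% |
| 10% | 92.5% | 95.0% | 97.5% | 100% |
| 15% | 88.8% | 92.5% | 96.3% | 100% |

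**6. ITSQ.** With a share p of leavers included, the two rules differ by p × (mean change in completers − mean change in leavers), where p is at most about 0.10. A gap of 10 points on the transformed score (assumed) would thus move the mean by at most about 1 point. The documents give neither the size nor the sign of such a gap.

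**The case against.** The two-point analysis is a stated choice. SAP 6.10.1 restricts these CGM variables to baseline and Visit 12, SAP 6.10.2 allows MMRM or ANCOVA for continuous CGM variables, and protocol 9.4.4 allows either for tertiary endpoints. Deriving values at Visits 7 and 9 does not oblige anyone to model them. This stands: a reader might infer that the SAP departs from the protocol, and it does not. What remains is the mismatch with the criterion in 6.2 and the table's CGM row, and the unused data.

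LOCF for mean glucose and variability is never stated outright. It arrives through the cross-reference to 6.2, and the restriction to two time points could be read as stating otherwise. Appendix 1 also rules out imputing missing CGM values, although that probably concerns single readings. The objection shows that the rule is unclear, and that is a reason to settle it.

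A reader might say that LOCF carries values from titration into a post-titration endpoint. Protocol 6.6.2 and 6.6.3 have doses reviewed at all visits through the 12 weeks, so the documents draw no such line. A fraction f below 1 is an assumption, and under it LOCF shrinks the estimate, which is conservative here.

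For ITSQ and DSAT, the table may list scheduled visits only, with the explicit text governing; its population column asks for a post-baseline observation, not specifically one at Visit 12. That reading is reasonable, but the SAP does not say which prevails. A reader might also infer that leaving out early leavers flatters the ITSQ result. The documents do not say how leavers would score.

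**Conclusion.** The point holds as a mismatch within the SAP and a missed, nearly free improvement. It is neither a protocol departure nor a demonstrated bias. Mean glucose and within- and between-day SD and CV do not fit the SAP's ANCOVA criterion, and their handling of dropouts differs from that of time in range. For ITSQ and DSAT, text and table define different analysis sets. For iAUC, the default LOCF and the Visit 12 row are unreconciled.

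The size is modest. At the planned dropout at most about 17 of 167 participants are touched, fewer if some leave without a usable value. Recovery of about 89-100% of the mean change rests wholly on the assumed ranges for d and f and on leavers having the same eventual effect. The endpoints concerned are ungated secondary or tertiary. The primary analysis, the gated analyses of HbA1c and 24-hour time in range, and the sample size are unaffected.

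**What to change.** 1. **Mean glucose, within- and between-day SD and CV.** Analyse with the 6.2 MMRM over Visits 7, 9 and 12 and report the Week 12 contrast. Amend 6.8.3 and 6.10.1 to match. Leave overall variability (Weeks 0-12) as it is.
2. **ITSQ and DSAT.** Change the post-baseline entry in Table ITSW.6.1 to Visit 12 or the early discontinuation visit, while on IP. This brings the table into line with SAP 6.8.3 and protocol 9.4.6.1.
3. **iAUC.** State which rule governs. Either keep LOCF and list the earlier visits that may supply a value, or keep Visit 12 only and say that LOCF does not apply. The second option is a completers-only analysis and should be labelled as one; simply deleting LOCF does not solve the dropout problem.

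The cost is a few lines of SAP wording and model code already specified for time in range. No new data are needed. Protocol 9.4.4 already allows item 1, and items 2 and 3 can stay within the ANCOVA that the protocol names.
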